10.6.5. Specific Toxicities/ Adverse Event Management

General guidelines for the management of specific toxicities that are considered to be associated with treatment of HIV patients.

Participants who permanently discontinue study drug for reasons of toxicity should be followed weekly until resolution of the AE and encouraged to complete the withdrawal and Follow-up study evaluations as noted in Section 8.5.3

10.6.5.1. Liver Chemistry Stopping and Follow-up Criteria

Liver chemistry threshold stopping criteria have been designed to assure participant safety and to evaluate liver event etiology during administration of study drug and the follow-up phase.

For a complete listing of stopping and follow-up criteria refer to Section 10.3.1.

10.6.5.2. Diarrhea

Participants with Grade 1 or 2 diarrhea may continue study treatment without interruption. Participants with diarrhea of any toxicity grade may be treated symptomatically with anti-motility agents; however, the recommended daily dose of the chosen anti-motility agent must not be exceeded. If symptoms persist or get worse on the recommended daily dose of the chosen anti-motility agent then the anti-motility agent must be discontinued and consultation made with the Medical Monitor.

For participants with Grade \geq 3 diarrhea that is unresponsive to the recommended dose of the anti-motility agents and for which an alternative etiology (e.g., infectious diarrhea) is not established, the treatment with the anti-motility agent and IP must be interrupted until resolution of diarrhea to Grade \leq 2 or Baseline, after which IP and background ART may be resumed after discussion and agreement with the Medical Monitor. If Grade 3 diarrhea recurs within 28 days upon the resumption of IP, the IP should be permanently discontinued and the participant withdrawn from the study. Any participant receiving at least one dose of CAB LA and /or RPV LA who discontinue IP / Withdraw will initiate treatment with HAART and enter the LTFU phase for 52 weeks of follow up.

If loperamide is used for treatment of diarrhea, local prescribing information should be followed with respect to dose and frequency of administration. Loperamide dosing should not exceed local prescribing information.

10.6.5.3. Seizures

Several cases of seizure have occurred during the cabotegravir program. These cases have alternate explanations for their occurrence. ViiV Healthcare has reviewed these cases in detail and does not believe they constitute a reasonable likelihood of causation associated with CAB. This assessment is supported by the lack of preclinical signal, class effect or known CNS mechanism, the relatively low frequency of seizures relative to expected rates in both healthy and HIV positive participants and clinical confounders in each case. The Sponsor considers the risk of developing seizures on the study as being no higher than that of the rest of the HIV-1 infected population.

Overall, there is not convincing evidence that cabotegravir exposure may be causally associated with seizure or with reduction of seizure threshold, due to the low frequency of reports, the confounders present in the cases received to date and lack of any preclinical signal or identified plausible mechanism. However, seizure and seizure-like events are considered as AEs of special interest for close monitoring in studies. Subjects with an unstable or poorly controlled seizure disorder will be excluded from study participation.

Seizures that occur on study should be managed according to the local guidelines on emergency seizure management which may include treatment with benzodiazepines, general supportive treatment, exclusion of metabolic and toxicological abnormalities using laboratory tests, septic workup and excluding underlying structural abnormalities with neuroimaging. Where seizures occur, the Sponsor would like to better characterize these occurrences to enable systematic analyses.

Investigators are requested to document and report seizure or possible seizure events promptly (within 24 hours of learning of the event) to the Sponsor for evaluation and onward reporting. Data should be documented on the appropriate eCRF seizure page.

10.6.5.4. Creatine Phosphokinase (CPK) Elevation

A Grade 3 or higher elevation in CPK should result in a repeat assessment within 2-4 weeks to ensure the result is transient or due to exercise and will not require a change in study treatment. A history regarding use of drugs known to cause increase of CPK (such as statins) physical activity or exercise preceding the CPK evaluation should be obtained.

Grade 4 elevations in CPK should have a repeat assessment after the participant has abstained from exercise for >24 hours. For persistent Grade 4 CPK elevations that are considered possibly or probably related to the IP, IP should be discontinued, and the participant withdrawn from the study. Any participant receiving at least one dose of CAB LA and /or RPV LA who discontinue IP / Withdraw will initiate treatment with HAART enter the LTFU phase for 52 weeks of follow-up.

10.6.5.5. Lipase Elevations and Pancreatitis

Participants with asymptomatic Grade 1 or 2 elevations in lipase may be followed closely for the development of symptoms.

Participants with asymptomatic Grade ≥ 3 elevations in lipase that are considered possibly or probably related to IP should have IP interrupted until serum lipase returns to Grade ≥ 2 . The lipase assay should be repeated within 2 weeks of any Grade ≥ 3 result. Participants with persistence of Grade ≥ 3 lipase in the absence of other diagnoses or reoccurrence of lipase elevation (at Grade ≥ 2) following reintroduction of IP should permanently discontinue IP.

Participants with a confirmed diagnosis of clinical pancreatitis that is considered possibly or probably related to IP should have IP held. After complete resolution of the episode, participants may be re-challenged with IP after discussion with the Medical Monitor, only if the Investigator has compelling evidence that the event was not caused by IP. Upon re-challenge, lipase determinations should be performed every 2 weeks for at least 6 weeks after re-initiation of treatment. With any elevation of lipase of Grade \geq 2 or any recurrence of symptoms, the participant should discontinue IP and be withdrawn from study.

Any participant receiving at least one dose of CAB LA and /or RPV LA who discontinue IP / Withdraw will initiate treatment with HAART and enter the LTFU phase for 52 weeks of follow up.

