10.6.1. Treatment Interruption Due to an Adverse Event

IP may be interrupted at the discretion of the Investigator and according to the severity of the AE. If one or more antiretroviral medications is held due to toxicity or adverse events, all antiretroviral medications must be held to reduce the risk of development of resistance considering both the length of the planned interruption and the pharmacokinetic half-life of each antiretroviral of the regimen, in a way to minimize the risk of development of resistance.

No toxicity-related dose reductions of IP will be allowed. IP should be restarted as soon as medically appropriate; in general, for oral dosing, this should be no longer than 14 days after discontinuation (unless Grade 3 or 4 toxicities persist). Any interruption in therapy during the Treatment Phase, oral dosing, of greater than 7 consecutive days must be discussed with and agreed by the Medical Monitor prior to resumption of therapy. The Medical Monitor must be contacted upon becoming aware of resumption in therapy, if therapy was resumed without prior approval. **IM dosing is expected to occur during the week in which the participant's projected visit falls (as according to the date of the first injection visit [Month 1] or called Target Date).** A +0 / -7 day window is **stipulated around the target date for dosing injections at Month 2.** A +7 / 7 day **window, from the projected target date, is allowable from the third injections forward.** Any interruption outside of this guidance MUST be discussed with the Medical Monitor prior to reinitiating IM IP.

Guidance is provided below on general participant management and IP interruptions based on the severity of the AE. All changes in the IP regimen must be accurately recorded in the participant's eCRF.

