10.6.2. Grade 1 or Grade 2 Toxicity/Adverse Event

Participants who develop a Grade 1 or Grade 2 AE or toxicity may continue IP at the discretion of the Investigator. (NOTE: See Section 10.6 Specific Toxicities/Adverse Event Management" for exceptions to this guideline). Participants who choose to withdraw from study due to a Grade 1 or 2 AE should have study withdrawal and followup evaluations completed.

Participants who develop ALT ≥3 times ULN while on study must consult with Medical Monitor prior to starting or continuing of CAB LA and RPV LA.

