10.6.3. Grade 3 Toxicity/Adverse Event

Participants who develop a Grade 3 AE or toxicity should be managed as follows:

- If the Investigator has compelling evidence that the Grade 3 AE or toxicity has not been caused by IP, dosing may continue after discussion with the Medical Monitor.
- Participants who develop a Grade 3 AE or toxicity, which the Investigator considers related or possibly related to the IP, should have the IP withheld and be rechecked each week until the AE returns to Grade 2. Once the AE is Grade □2, IP may be re-started.
- Should the same Grade 3 AE recur within 28 days in the same participant, the IP should be permanently discontinued and the participant withdrawn from study.
- Participants experiencing Grade 3 AEs requiring permanent discontinuation of IP should be followed weekly until resolution of the AE and to have withdrawal study evaluations completed. A follow-up visit should be performed 2-4 weeks after the last dose of IP. Any participant receiving at least one dose of CAB LA and /or RPV LA who discontinue IP / Withdraw will initiate treatment with HAART and enter the Long-Term Follow-Up Phase for 52 weeks of follow up.
- Participants with Grade 3 asymptomatic laboratory abnormalities should be investigated for all potential non-drug related causes, and, following discussion with the Medical Monitor, may continue IP if the Investigator has compelling evidence that the toxicity is not related to IP, with the exception of liver chemistry stopping criteria (See Section 10.6.5.1). Isolated Grade 3 lipid abnormalities do not require withdrawal of IP.

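### Section 10.6.5.5 prints the lipase release condition as a lower bound (Grade ≥ 2) where an upper bound is needed

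*Protocol*

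**What the plan says.** Lipase belongs to the routine chemistry panel (Protocol 8.4.4), and 10.6.5.5 is the section that governs a raised result. It sets out these steps:

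- Low grades: "Participants with asymptomatic Grade 1 or 2 elevations in lipase may be followed closely for the development of symptoms". No interruption is called for.
- Asymptomatic Grade 3 or higher, possibly or probably related: participants "should have IP interrupted until serum lipase returns to Grade ≥ 2".
- Repeat test: "The lipase assay should be repeated within 2 weeks of any Grade ≥ 3 result".
- Permanent stop, for either of two groups. One is "Participants with persistence of Grade ≥ 3 lipase in the absence of other diagnoses". The other is participants whose lipase rises again to Grade 2 or above "following reintroduction of IP should permanently discontinue IP".

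The general rules of the same appendix also apply. For Grade 1 and 2 events, 10.6.2 states: "Participants who develop a Grade 1 or Grade 2 AE or toxicity may continue IP at the discretion of the Investigator". For a related Grade 3 event, 10.6.3 says the participant "should have the IP withheld and be rechecked each week until the AE returns to Grade 2", after which restart is allowed. For oral dosing, 10.6.1 expects restart within 14 days in general, unless Grade 3 or 4 persists. Section 10.6.5.2, the parallel specific rule for diarrhea, ends the hold at Grade ≤ 2 or Baseline.

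**The concern.** The hold exists because lipase is too high, so the condition that ends it should say how low the value must fall. The printed sign says how high it must be. A site that goes to the lipase section for the release threshold therefore finds one that points the wrong way and differs from the rest of the appendix.

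At stake is the clarity of a safety instruction. It matters most during oral lead-in or bridging, where 7.1.4 allows interruptions for toxicity and where an unclear release bears on how long daily antiretroviral therapy is held. No estimate or test in the trial depends on it.

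**Working it through.** The plan gives no calculated figure to reproduce here. The check applies the printed condition to the protocol's own lipase grades.

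**Inputs.** Lipase bands from the DAIDS table in Protocol 10.2, in multiples of ULN: Grade 1 is 1.1 to <1.5, Grade 2 is 1.5 to <3.0, Grade 3 is 3.0 to <5.0, Grade 4 is ≥ 5.0. The hold starts at Grade ≥ 3 (10.6.5.5).

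**Test.** Each repeat value is graded, then compared with the printed release (Grade ≥ 2) and with the same rule with the sign turned (Grade ≤ 2).

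| Repeat lipase (x ULN) | Grade | Printed, literal: ≥ 2 | Sign turned: ≤ 2 |
|---|---|---|---|
| 0.9 | below 1 | not released | released |
| 1.1 | 1 | not released | released |
| 1.49 | 1 | not released | released |
| 1.5 | 2 | released | released |
| 2.9 | 2 | released | released |
| 3.0 | 3 | released | held |
| 4.9 | 3 | released | held |
| 5.0 | 4 | released | held |
| 8 | 4 | released | held |

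**Results.**

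1. Three grade levels lie below the trigger: Grade 2, Grade 1 and below Grade 1. The printed condition is met by one of them (Grade 2). Values under 1.5 x ULN do not meet it.
2. The printed condition is also met by Grades 3 and 4, the values that start the hold. Persistent Grade 3 without another diagnosis would then satisfy the release and the permanent-stop rule in the same paragraph. Related Grade 4 is not part of that clash, because 10.6.4 discontinues it permanently unless there is compelling evidence that it is unrelated.
3. With the sign turned, every value under 3.0 x ULN is released and every value at or above it is held. This agrees with 10.6.5.2, with 10.6.3, and with an opening sentence that asks only for close follow-up at Grades 1 and 2.

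**Timing for injections.** Take the shortest calendar month as 28 days and the shortest two months as 59 days, with the dosing windows in 1.3. The shortest gap to the next injection is 28 − 7 = 21 days (Dose 1 to 2), 59 − 7 = 52 days (Dose 2 to 3) and 59 − 14 = 45 days (Dose 3 onward). If the 14 days for the repeat assay run from the visit sample, the repeat comes at least 21 − 14 = 7, 52 − 14 = 38 and 45 − 14 = 31 days before that injection. This margin does not apply to daily oral dosing.

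**The case against.** The strongest objection is that the point rests on one comparison sign in machine-read text. Signs in this text are sometimes damaged: the restart sentence in 10.6.3 has lost its operator, the bilirubin item in the liver follow-up table of 10.3.1 shows a superscript where a comparison sign belongs, and a minus sign is missing from the injection window in 10.6.1. This stands as a reason to check the source PDF first. It does not defeat the point. Those examples are lost or substituted symbols rather than clear inversions, the ≤ in 10.6.5.2 came through, and the other ≥ signs in the lipase paragraph make sense as printed.

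A second objection is that no clinician would apply the literal reading. A hold triggered at Grade 3 cannot sensibly be ended by the value that triggered it, and in ordinary usage returning to Grade 2 includes a fall through Grade 2 to something lower. Section 10.6.3 uses that same phrase. This stands too, and it limits the consequence. It does not make the printed sign correct.

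A reader might infer that a participant whose lipase has normalised stays on hold with no way back. The documents do not support that. Section 10.6.1 says IP should restart as soon as medically appropriate, 10.6.3 supplies a restart rule for related Grade 3 events, and interruption or resumption is handled with the Medical Monitor (1.3 footnote i, 7.1.4, 10.6.1).

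**Conclusion.** The point holds as a minor wording error in an operative safety threshold. As printed, the condition is a lower bound: read literally it admits the triggering grades, excludes values under 1.5 x ULN, and is inconsistent with 10.6.5.2, 10.6.3 and the section's opening sentence.

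The practical effect is small, because the general rules and Medical Monitor contact leave a workable route to restart, and the repeat assay falls due before the next injection. How many participants it could touch cannot be stated. The conclusion assumes that the source PDF prints the same sign as the text reviewed here.

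**What to change.** Check the sign in the source PDF. If it prints ≥, change the release condition in 10.6.5.5 to Grade ≤ 2. Leave the Grade ≥ 3 persistence stop and the Grade ≥ 2 recurrence stop unchanged.

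One detail deserves a deliberate decision. With Grade ≤ 2, a participant may restart at Grade 2, which is also the level that counts as recurrence after reintroduction. The sponsor could choose Grade ≤ 1 to avoid this, but the release would then be stricter than in 10.6.3 and 10.6.5.2.

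The cost is one character, carried in the next protocol amendment with the ethics approval that 10.1.1 requires. No assessment is added and no analysis changes. Until then, sites can follow 10.6.3 together with the Medical Monitor.

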10.6.5.6. Decline in Renal Function

Participants who experience an increase in serum creatinine from Baseline of 45 micromoles/liter (μ Mol/L) (or 0.5 milligrams/deciliter [mg/dL]) should return for a confirmatory assessment within 2 to 4 weeks. A urinalysis and urine albumin/creatinine and urine total protein/albumin ratios should also be done at this confirmatory visit. If the creatinine increase is confirmed, the Investigator should contact the study medical monitor to discuss additional follow-up and medical management.

Participants who have a decline in the estimated GFR (using the CKD-EPI method) of >50% from Baseline must return for a confirmatory assessment as soon as possible [Levey, 2009]. A urinalysis and urine albumin/creatinine and urine protein/creatinine ratios should also be done at this confirmatory visit. If the estimated GFR has declined by >50% (confirmed), then study drug should be withheld and the Investigator should contact the study medical monitor to discuss the rationale for restarting study drugs (if appropriate). Consideration for confounding factors (e.g., background therapy, other medications, dehydration, concurrent conditions) should be taken into account, and a nephrology consult may be obtained.

10.6.5.7. Proximal Renal Tubule Dysfunctions (PRTD)

PRTD is defined as:

Confirmed rise in serum creatinine of ≥ 0.5 mg/dL from Baseline AND serum phosphate < 2.0 mg/dL;

Either of the above accompanied by any two of the following:

Glycosuria (≥250 mg/dL) in a non-diabetic;

Low serum potassium (<3 mEq/L);

Low serum bicarbonate (<19 mEq/L).

Participants meeting criteria for PRTD must return for a confirmatory assessment within 2 weeks of diagnosis. A urinalysis should also be performed at the time of the confirmatory assessment. If PRTD is confirmed participants should have study drug withheld and the Investigator should contact the Study medical monitor to discuss the rationale for restarting study drugs (if appropriate). Consideration for confounding factors (e.g., NRTI backbone, other medications, dehydration, concurrent conditions) should be taken into account, and a nephrology consult may be obtained. If study drug is reinitiated, it should have been withheld for no more than 4 weeks.

10.6.5.8. Injection Site Reactions (ISRs)

Injection site reactions will be managed through investigator assessment throughout the study. All ISRs that are either serious, Grade 3 or higher, or persisting beyond 2 weeks

must be discussed with the Medical Monitor to determine etiology and assess appropriate continued study participation.

Digital photographs may be documented where possible on all participants who have an injection site reaction, with observable findings, that is either serious or Grade 3 or higher, or that persists beyond 2 weeks. Dermatology will be consulted on all participants who have an injection site reaction considered serious, Grade 3 or above, or if clinically significant and persistent beyond 30 days and others if the Investigator or Medical Monitor feels it is medically necessary.

Details regarding photo collection and any other follow up will be given by the Medical Monitor at the time of assessment.

ISR discomfort can be managed symptomatically (e.g., cold/warm compress, acetaminophen, ibuprofen) if the reaction is interfering with the participant's ability to perform activities of daily living. The required intervention should be documented on the appropriate eCRF page.

10.6.5.9. Allergic reaction

Participants may continue study drug for Grade 1 or 2 allergic reactions at the discretion of the Investigator. The participant should be advised to contact the Investigator immediately if there is any worsening of symptoms or if further systemic signs or symptoms develop. Antihistamines, topical corticosteroids, or antipruritic agents may be prescribed.

Participants with Grade \geq 3 allergic reactions that are considered to be possibly or probably related to the study drug should permanently discontinue the CAB LA + RPV LA regimen and the participant should be withdrawn from the study. Participants should be treated as clinically appropriate and followed until resolution of the AE.

10.6.5.10. Rash Without HSR Symptoms

Including serious skin reactions such as Stevens-Johnson Syndrome, Toxic Epidermal Necrolysis, Erythema Multiforme or rash with significant liver dysfunction.

Participants should be instructed to contact the Investigator as soon as possible if they develop a rash on study.

As many products also cause rash and/or serious skin reactions, all other medicinal products that the participant is receiving should also be reviewed and discontinued as appropriate.

The following guidance is provided for clinical management of participants who experience rash alone in the absence of systemic or allergic symptoms or signs of mucosal or target lesions.

CAB is an analogue of DTG and mild to moderate rash is an expected adverse reaction for DTG-containing ART. Episodes generally occur within the first 10 weeks of

treatment, rarely require interruptions or discontinuations of therapy and tend to resolve within two to three weeks. No instances of serious skin reaction, including SJS, TEN and erythema multiforme, have been reported for DTG in clinical trials. For further characterization of HSR and rash observed with DTG-containing ART, please see the current version of the CAB IB. Rash is an adverse drug reaction (ADR) for RPV. In clinical trials, most rashes emerged during the first 4 weeks of treatment, were transient, and usually mild (Grade 1) to moderate (Grade 2). There were no Grade 4 rashes and none were serious. Treatment related Grade 3 rash was reported in 0.1% of participants in the RPV group. Treatment related rash led to permanent discontinuation in 0.1% of participants in the RPV group. No cases of erythema multiforme, SJS or TEN have been reported during clinical development of RPV.

Participants with an isolated Grade 1 rash may continue study drug at the Investigator's discretion. The participant should be advised to contact the Investigator immediately if there is any worsening of the rash, if any systemic signs or symptoms appear, or if mucosal involvement develops.

Participants may continue study drug for an isolated Grade 2 rash. However, study drug (and all other concurrent medication(s) suspected in the Investigators causality assessment) should be permanently discontinued for any Grade ≥ 2 rash that is associated with an increase in ALT. The participant should be advised to contact the physician immediately if rash fails to resolve (after more than 2 weeks), if there is any worsening of the rash, if any systemic signs or allergic symptoms develop, or if mucosal involvement develops.

